#### 5.2.4.1 Arm 2: Nivolumab Administration

Nivolumab 240mg will be administered as a 30 minute IV infusion on Day 1, 15, and 29 of each 42 day cycle. Nivolumab should not be given any earlier than 12 days from the previous dose. Sites should make every effort to target infusion timing to be as close to 30 minutes as possible. However, given the variability of infusion pumps from site to site, a window of +/-10 minutes is permitted (i.e., infusion time is 30 minutes: +/-10 min). Treatment will continue for up to 4 cycles, in the absence of prohibitive toxicities or disease progression.

#### 5.2.4.2 Arm 2: Ipilimumab Administration

Ipilimumab 1mg/kg will be administered as a 30 minute IV infusion on Day 1 of each 42 day cycle. Sites should make every effort to target infusion timing to be as close to 30 minutes as possible. However, given the variability of infusion pumps from site to site, a window of +/-10 minutes is permitted (i.e., infusion time is 30 minutes: +/-10 min). Treatment will continue for up to 4 cycles, in the absence of prohibitive toxicities or disease progression.

On day 1 of cycle 1, nivolumab will be given first, followed by 30 minutes of monitoring, and then ipilimumab given second, followed by 30 minutes of monitoring. If the subject does not have an infusion reaction during the first cycle, the post-ipilimumab monitoring may be discontinued for subsequent cycles at the discretion of the treating physician. Day 1 monitoring between the nivolumab/ ipilimumab infusions will continue throughout all 4 cycles. Post nivolumab monitoring on days 15 and 29 is not mandatory and should follow the guidelines of the local infusion center.

#### 5.3 Concomitant Medications

All concomitant medications received within 28 days before the first dose of trial treatment and 30 days after the last dose of trial treatment should be recorded. Concomitant medications administered more than 30 days after the last dose of trial treatment should be recorded for serious adverse events (SAE) as defined in Section 11.1.2.

#### 5.3.1 Allowed Concomitant Medications

All treatments that the site investigator considers necessary for a subject's welfare may be administered at the discretion of the site investigator in keeping with the community standards of medical care. All

concomitant medication will be recorded on the case report form (CRF) including all prescription, overthe-counter (OTC), herbal supplements, and IV medications and fluids. If changes occur during the trial period, documentation of drug dosage, frequency, route, and date may also be included on the CRF.

#### 5.3.2 Prohibited Concomitant Medications

Medications or vaccinations specifically prohibited in the exclusion criteria are not allowed during the ongoing trial. If there is a clinical indication for one of these or other medications or vaccinations specifically prohibited during the trial, discontinuation from trial therapy or vaccination may be required. The site investigator should discuss any questions regarding this with BTCRC AHQ who will then communicate with the sponsor-investigator and Bristol-Myers Squibb Clinical team regarding the situation. The final decision on any supportive therapy or vaccination rests with the site investigator and/or the subject's primary physician. There are no prohibited therapies during the Post-Treatment Follow-up Phase.

Subjects are prohibited from receiving the following therapies during the Screening and Treatment Phase of this trial:

- Antineoplastic systemic chemotherapy or biological therapy not specified in this protocol
- Immunotherapy not specified in this protocol
- Chemotherapy not specified in this protocol
- Investigational agents other than nivolumab or ipilimumab
- Radiation therapy
- Live vaccines within 30 days prior to the first dose of trial treatment and while participating in the trial. Examples of live vaccines include, but are not limited to, the following: measles, mumps, rubella, varicella/zoster, chicken pox, yellow fever, rabies, BCG, and typhoid (oral) vaccine. Seasonal influenza vaccines for injection are generally killed virus vaccines and are allowed; however intranasal influenza vaccines (e.g. Flu-Mist®) are live attenuated vaccines, and are not allowed.
- Systemic glucocorticoids (>10 mg prednisone equivalent) for any purpose other than to modulate symptoms from an event of clinical interest of suspected immunologic etiology. Brief, limited use of systemic corticosteroids (≤7 days) are permitted where such use is considered standard of care (e.g. as premedication for contrast allergy or for COPD exacerbation). Inhaled or topical steroids, and adrenal replacement doses of steroids (for example prednisone 10mg daily) are permitted while on study.

Subjects who, in the assessment by the site investigator, require the use of any of the aforementioned treatments for clinical management should be removed from the trial.

There are no prohibited therapies during the Post-Treatment Follow-up Phase.

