#### 5.5.3 Use in Pregnancy

If a subject inadvertently becomes pregnant while on treatment with nivolumab or ipilimumab, the subject will immediately be removed from the study. The site will contact the subject at least monthly and document the subject's status until the pregnancy has been completed or terminated. The outcome of the pregnancy will be reported to the Big Ten Research Consortium (BTCRC) within 24 hours of discovery of event and BTCRC will notify the sponsor-investigator and Bristol-Myers Squibb within 24 hours if the outcome is a serious adverse experience (e.g., death, abortion, congenital anomaly, or other disabling or life-threatening complication to the mother or newborn). The site investigator will make every effort to obtain permission to follow the outcome of the pregnancy and report the condition of the fetus or newborn to BTCRC who will report to Bristol-Myers Squibb. If a male subject impregnates his female partner the study personnel at the site must be informed immediately and the pregnancy reported to the BTCRC who will report to Bristol-Myers Squibb and followed as described above.

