#### 6.2 Subject Withdrawal/Discontinuation Criteria

Subjects may withdraw consent at any time for any reason or be withdrawn from the trial at the discretion of the site investigator should any untoward effect occur. In addition, a subject may be withdrawn by the sponsor-investigator or BTCRC if enrollment into the trial is inappropriate, the trial plan is violated, or for administrative and/or other safety reasons. Specific details regarding discontinuation or withdrawal are provided below.

A subject must be discontinued from the trial treatment for any of the following reasons:

- Confirmed radiographic disease progression by RECIST 1.1 criteria
- Unacceptable adverse experiences as described in Section 5.3 and 11.1

- Intercurrent illness that prevents further administration of treatment
- Site investigator's decision to withdraw the subject
- A female subject has a confirmed positive serum/urine pregnancy test
- Noncompliance with trial treatment or procedure requirements
- Completed 6 months of treatment with protocol therapy
- Subject refuses further treatment
- If a subject has a treatment delay of more than 12 weeks from last infusion. See section 6.1.

A subject must be discontinued from the trial for any of the following reasons:

- Administrative reasons
- The subject or legal representative (such as a parent or legal guardian) withdraws consent.
- The subject is lost to follow-up

The End of Treatment and Follow-up visit procedures are listed in Section 7 (Study Schedule of Events and Visit Requirements). After the end of treatment, each subject will be followed for 100 days for adverse event monitoring (serious adverse events will be collected for 100 days after the end of treatment as described in Section 12.2.2). Subjects who discontinue for reasons other than progressive disease will have post-treatment follow-up for disease status until disease progression, initiating a non-study cancer treatment, withdrawing consent or becoming lost to follow-up. After documented disease progression each subject will be followed for survival for up to 2 years, withdrawal of consent, or the end of the study, whichever occurs first.

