#### 6.3 **Protocol Discontinuation**

If a subject decides to withdraw from the study (and not just from protocol therapy) all efforts should be made to complete the final study assessments. The site study team should contact the subject by telephone or through a clinic visit to determine the reason for the study withdrawal. If the reason for withdrawal is an adverse event, it will be recorded on the eCRF.

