## **10.8.6 Progression Free Survival**

A measurement from the date of randomization until the criteria for disease progression is met as defined by RECIST 1.1 or death occurs. Subjects who have not progressed will be right-censored at the date of the last disease evaluation.

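### Sections 5.3.2 and 5.5.3 direct, and the opening of 6.2 permits, removal from the trial where other sections only stop treatment; if sites follow the removal wording, PFS and OS follow-up can end without withdrawn consent.

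*Combined protocol and SAP*

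**What the plan says.** All references are to the combined protocol and SAP.

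**Wording that takes subjects off the trial**
- 5.3.2, after the list of prohibited therapies: subjects who, in the site investigator's assessment, "require the use of any of the aforementioned treatments for clinical management should be removed from the trial".
- 5.5.3: on pregnancy during treatment, "the subject will immediately be removed from the study".
- 6.2, opening paragraph: subjects may "be withdrawn from the trial at the discretion of the site investigator should any untoward effect occur". The sponsor-investigator or BTCRC may also withdraw a subject for inappropriate enrollment or violation of the trial plan.

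**Wording that stops treatment only**
- 5.3.2, first paragraph: for prohibited medications or vaccinations, "discontinuation from trial therapy or vaccination may be required".
- 6.2, first list (reasons to discontinue trial treatment): it includes unacceptable adverse experiences, noncompliance, the site investigator's decision and "A female subject has a confirmed positive serum/urine pregnancy test".
- 12.1.5: on pregnancy, the study drug is discontinued.

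**The protocol treats the two as different.** The second list in 6.2 is headed "A subject must be discontinued from the trial for any of the following reasons" and holds only administrative reasons, withdrawn consent and loss to follow-up. Section 6.3 begins "If a subject decides to withdraw from the study (and not just from protocol therapy", which draws the same line.

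**Follow-up and analysis.** Under 6.2 and 8.5, subjects who discontinue without progression continue disease follow-up until progression, non-study cancer treatment, withdrawn consent or loss. For PFS, 10.8.6 states: "Subjects who have not progressed will be right-censored at the date of the last disease evaluation". Section 10.8.8 gives no censoring rule for OS. Section 13 rules out imputation, and 13.7.1 and 13.7.2 analyse PFS and OS in the randomized population.

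**The concern.** The same trigger leads to different follow-up depending on which section a site reads. A subject taken off study drug keeps having scans; a subject removed from the trial, in the plain sense of the words, does not. Take a subject who needs systemic steroid above the 5.3.2 limit for longer than the permitted brief course, for a COPD exacerbation. Read literally, 5.3.2 ends all outcome collection for that subject, although consent was not withdrawn and no cancer therapy was started.

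Such a subject stays in the randomized population and is censored for PFS at the last scan. That is harmless only if removal is unrelated to prognosis. Subjects removed for lung problems, toxicity or poor adherence could plausibly do worse than those who stay. Each arm's primary test is against a fixed historical rate, so no concurrent control shares the bias, and no sensitivity analysis for early removal is planned. Outcomes that were never collected cannot be recovered at analysis.

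**Working it through.** **1. The text, trigger by trigger**

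| Trigger | Off-trial wording | Treatment-only wording | Status of removal |
|---|---|---|---|
| Prohibited treatment | 5.3.2, after the list | 5.3.2, first paragraph | directed |
| Pregnancy | 5.5.3 | 6.2 first list; 12.1.5 | directed |
| Untoward effect | 6.2 opening | 6.2 first list | permitted |
| Plan violated | 6.2 opening | 6.2 first list (noncompliance) | permitted |

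Each trigger has text on both sides. No section says which prevails, or that a subject removed from the trial stays in follow-up.

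**2. The plan's own figures (13.3).** Inputs: one-sided alpha 0.10, power 80%, 30% vs 44% (Arm 1), 44% vs 59% (Arm 2), 5% non-evaluable. One-sample normal approximation: n = [1.2816·√(p0(1−p0)) + 0.8416·√(p1(1−p1))]² / (p1−p0)².
- Arm 1: (0.5873 + 0.4178)² / 0.14² = 51.5; stated 51, power at 51 is 79.7%.
- Arm 2: (0.6362 + 0.4139)² / 0.15² = 49.0; stated 48, power at 48 is 79.4%.
- 51/0.95 = 53.7, so 54; 48/0.95 = 50.5, so 51.

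The stated sample sizes are not in error.

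**3. Effect of removal (illustration).** From the documents: n = 51 and 48, the null rates, 24 months of accrual within 48 months (administrative censoring at 24-48 months), and treatment for up to 24 weeks, about 5.5 months. Assumed: exponential PFS; a fraction f removed at a uniform time over 0-5.5 months if still progression-free; PFS hazard r times that of the rest. The base hazard λ solves (1−f)·exp(−18λ) + f·exp(−18λr) = p0, so the true 18-month rate stays at the null. The test rejects if [log(−log p0) − log(−log S)] / √(G/(log S)²) > 1.2816, where S is the Kaplan-Meier estimate at 18 months and G the Greenwood sum. This stands in for the plan's sign test for censored data. There were 6,000 replicates, so the Monte Carlo error near 0.10 is √(0.10·0.90/6000) = 0.004.

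| f | r | Arm 1: mean estimate (true 30%) | Arm 1: type I error | Arm 2: mean estimate (true 44%) | Arm 2: type I error |
|---|---|---|---|---|---|
| 0 | – | 30.0% | 0.102 | 43.9% | 0.098 |
| 5% | 2 | 30.8% | 0.120 | 44.8% | 0.110 |
| 10% | 1 | 29.9% | 0.088 | 44.0% | 0.090 |
| 10% | 2 | 31.7% | 0.145 | 45.9% | 0.140 |
| 10% | 3 | 32.0% | 0.150 | 46.9% | 0.171 |
| 20% | 2 | 33.4% | 0.203 | 48.0% | 0.206 |

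Over f = 5-20% and r = 1.5-3, type I error runs from about 0.10 to 0.27. With r = 1 and f = 10%, power falls from about 0.80 to 0.74.

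**4. Scale.** Ten percent of the enrolled arms is 0.10·54 = 5.4 and 0.10·51 = 5.1, about five subjects each. The target effects are 44−30 = 14 and 59−44 = 15 points.

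**The case against.** The strongest reply is that 6.2 already settles the matter. Its opening paragraph only permits withdrawal and defers to the details below it, where toxicity, intercurrent illness, noncompliance, pregnancy and the investigator's decision are all reasons to stop treatment. This stands. A reader might infer that subjects with toxicity or deviations must leave the trial, but the documents do not say so. It does not dispose of 5.3.2 and 5.5.3, which direct removal.

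For 5.3.2, the sentence after the removal instruction says that nothing is prohibited in post-treatment follow-up, which fits moving the subject into that phase. The reading is reasonable, but a site has to infer it.

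The affected group may be small. Five of the seven prohibited items are other systemic cancer therapy, immunotherapy, chemotherapy, investigational agents and radiation. Where these are non-study cancer treatment, disease follow-up ends anyway. Steroids for a suspected immune event are exempt. Pregnancy will probably add few cases with little prognostic content, and 5.5.3 keeps monthly contact until the pregnancy ends. All of this limits the size; none of it removes the contradiction.

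A reader might also infer that removed subjects' adverse events vanish from the safety tables. The documents do not support that. Sections 12.2.1 and 12.2.2.1 collect AEs and SAEs to 100 days after study drug stops, or until new anti-cancer treatment if earlier. Section 8.4 schedules a safety visit whatever the reason for stopping, and 6.2 asks for final-visit procedures at withdrawal.

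**Conclusion.** The contradiction is real and bears on ascertainment of the primary endpoint. For prohibited treatment and pregnancy the protocol directs removal in one place and stops only treatment in another; for untoward effects and plan violations it permits withdrawal while listing the corresponding reasons under treatment discontinuation.

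The stronger reading, that PFS and OS are already censored informatively, does not follow. Bias needs three things that the documents do not establish: sites act on the removal wording, enough subjects are affected, and those removed have a worse prognosis. Under the assumed 5-10% removed at twice the PFS hazard, the estimate rises by roughly 1-2 points against targets of 14 and 15, and type I error goes from 0.10 to about 0.11-0.145. Removal unrelated to prognosis slightly lowers type I error and costs power. If removed subjects did better than the rest, the bias would run the other way. OS is exposed in the same manner, but its size was not calculated.

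**What to change.** - Reconcile 5.3.2, 5.5.3, 6.2 and 12.1.5 so that each trigger has one stated consequence.
- Define *off study drug* and *off study* as separate states.
- Limit *off study* to withdrawn consent for follow-up, loss to follow-up, and study end or administrative closure.
- State that all other subjects stay in scheduled imaging, safety and survival follow-up, whatever the reason treatment stopped. Survival follow-up in 6.2 and 8.5 is written only for subjects with documented progression, so it needs to be stated for those who stop without it.

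The amendment should leave alone whether and when treatment stops. In particular, prohibited medication should not simply be added to the mandatory treatment-discontinuation list in 6.2: the first paragraph of 5.3.2 says only that stopping may be required, and that clinical question belongs to the sponsor.

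Cost: a wording amendment, plus a few additional scans and contacts already on the standard follow-up schedule.

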#### 5.4 Supportive Care

Subjects should receive appropriate supportive care measures as deemed necessary by the site investigator. Suggested supportive care measures for the management of adverse events with potential immunologic etiology are outlined below. Where appropriate, these guidelines include the use of oral or intravenous treatment with corticosteroids as well as additional anti-inflammatory agents if symptoms do not improve with administration of corticosteroids. Note that several courses of steroid tapering may

be necessary as symptoms may worsen when the steroid dose is decreased. For each disorder, attempts should be made to rule out other causes such as metastatic disease or bacterial or viral infection, which might require additional supportive care. The treatment guidelines are intended to be applied when the investigator determines the events to be related to nivolumab or ipilimumab.

# 5.4.1 Suggested supportive care measures for the management of adverse events that are related to nivolumab or ipilimumab

Immuno-oncology (I-O) agents are associated with AEs that can differ in severity and duration than AEs caused by other therapeutic classes. Nivolumab and ipilimumab are considered immuno-oncology agents in this protocol. Early recognition and management of AEs associated with immuno-oncology agents may mitigate severe toxicity. Management algorithms have been developed to assist investigators in assessing and managing the following groups of AEs: Gastrointestinal, Renal, Pulmonary, Hepatic, Endocrinopathies, Skin, Neurological.

For subjects expected to require more than 4 weeks of corticosteroids or other immunosuppressants to manage an AE, consider recommendations provided in the algorithms. These algorithms are found in Appendix 1. The guidance provided in these algorithms should not replace the Investigator's medical judgment but should complement it.

Patients on IV steroids may be switched to an equivalent dose of oral corticosteroids (e.g. prednisone) at start of tapering or earlier, once sustained clinical improvement is observed. Lower bioavailability of oral corticosteroids should be taken into account when switching to the equivalent dose of oral corticosteroids.

Patients who are started on steroids for management of an immune-related event should not resume immunotherapy until steroids have been tapered to  $\leq$  prednisone 10mg daily or an equivalent dose of an alternative corticosteroid.

• **Management of Infusion Reactions:** Acute infusion reactions (which can include cytokine release syndrome, angioedema, or anaphylaxis) are different from allergic/hypersensitive reactions, although some of the manifestations are common to both AEs.

The table below shows treatment guidelines for subjects who experience an infusion reaction associated with administration of nivolumab.

Management of Infusion Related Reaction (IRR), Allergic Reaction, Hypersensitivity reaction or Bronchospasm from Nivolumab or Ipilimumab

Description	Action
CTCAE Grade 1 IRR,	
allergic reaction or	Remain at bedside and monitor subject until recovery from symptoms.
bronchospasm 	
	Stop the infusion, begin an IV infusion of normal saline, and treat the
CTCAE Grade 2 IRR,	subject with diphenhydramine 50 mg IV (or equivalent) and/or
allergic reaction or paracetamol 325 to 1000 mg (acetaminophen); remain at bedsi	
bronchospasm 	monitor subject until resolution of symptoms. Corticosteroid or
	bronchodilator therapy may also be administered as appropriate. If the

	infusion is interrupted, then restart the infusion at 50% of the original infusion rate when symptoms resolve; if no further complications ensue after 30 minutes, the rate may be increased to 100% of the original infusion rate. Monitor subject closely. If symptoms recur, then no further nivolumab will be administered at that visit. Administer diphenhydramine 50 mg IV, and remain at bedside and monitor the subject until resolution of symptoms. The amount of study drug infused	
	must be recorded on the electronic case report form (eCRF).	
CTCAE Grade 3 or 4 IRR, allergic reaction, bronchospasm or hypersensitivity reaction 	Immediately discontinue infusion of nivolumab. Begin an IV infusion of normal saline, and treat the subject as follows. Recommend bronchodilators, epinephrine 0.2 to 1 mg of a 1:1,000 solution for subcutaneous administration or 0.1 to 0.25 mg of a 1:10,000 solution injected slowly for IV administration, and/or diphenhydramine 50 mg IV with methylprednisolone 100 mg IV (or equivalent), as needed. Subject should be monitored until the investigator is comfortable that the symptoms will not recur. Nivolumab or ipilimumab will be permanently discontinued . Investigators should follow their institutional guidelines for the treatment of anaphylaxis. Remain at bedside and monitor subject until recovery from symptoms. In the case of late-occurring hypersensitivity symptoms (eg, appearance of a localized or generalized pruritis within 1 week after treatment), symptomatic treatment may be given (eg, oral antihistamine, or corticosteroids).	
 For any <grade 2="" 5.1.2="" allergic="" bronchospasm="" for="" irr="" or="" premedication<="" reaction="" recommended="" section="" see="" td=""></grade>		

For any  $\leq$ Grade 2 IRR, allergic reaction or bronchospasm, see Section 5.1.2 for recommended premedication for subsequent infusions.

Hypersensitivity reactions included in CTCAEv4 include anaphylaxis, Stevens-Johnson syndrome and toxic epidermal necrolysis; in the case of late-occurring hypersensitivity symptoms (e.g., appearance of a localized or generalized pruritis within 1 week after treatment), symptomatic treatment may be given (e.g., oral antihistamine, or corticosteroids).

